Assessing the Effectiveness of Self- and Clinician-administered Crisis Response Planning for Suicide Risk

NCT Number: 2020B0414-B

Date: 5/18/2021

Assessing the Effectiveness of Self- and Clinician-administered Crisis Response Planning for Suicide Risk

1. Objectives

The aim of the current project is to compare the use and preliminary effectiveness of a self-administered version of the Crisis Response Plan (CRP) in decreasing suicidal/death ideation and distress and increasing positive affect when compared to a clinician-administered version of the protocol in a sample of 150 military Veterans experiencing current death or suicidal ideation. As the aim of examining the effectiveness self- and clinician-administered versions of the CRP is exploratory, no hypotheses are proposed. However, the results of this research will inform best practices for administration of the CRP in future research and clinical contexts.

2. Background and Rationale

In response to enhanced detection of suicide risk, there is a need to identify psychotherapeutic interventions targeting suicide risk among military veterans who may be unable or unwilling to seek follow-up mental health services. Indeed, reasons for refusal to seek mental health services among veterans include public and self-stigma (Held & Owens, 2013), adherence to masculine norms (Burns & Mahalik, 2011). However, Wilson et al. (2008) observed that the majority of Army soldiers who were unwilling to speak to a clinician about mental health care were willing to utilize technology-based approaches to mental health care.

2.1 Crisis Response Planning for Suicide Risk. Crisis Response Planning (CRP) is a brief, psychotherapeutic intervention with demonstrated efficacy in increasing positive affect, decreasing negative affect and psychiatric hospitalizations, and reducing suicide attempts by 76% in military personnel when compared to contracts to safety (Bryan et al., 2017, 2018). Given the efficacy and flexibility of the intervention, CRP has been successfully implemented as part of interventions targeting PTSD and suicide risk (Bryan and Rudd, 2018; Rozek & Bryan, 2020). **This proposed research is aimed at examining the efficacy of the intervention in reducing suicidal ideation, distress, and negative affect and increasing positive affect when compared to a self-administered version.**

CRP is focused on creating personalized set of steps for individuals to follow in case of a crisis and includes individuals' personal warning signs of distress, behavioral coping strategies, reasons for living, social supports to contact, and contact information for professional services, including emergency services. Personalization of the CRP is encouraged, and individuals are instructed to handwrite each step of the CRP on an index card. Additionally, clinicians instruct patients to review the CRP periodically in order to mentally rehearse each step and change the contact of the CRP as needed (e.g., after using the CRP, a behavioral coping strategy was found to be unhelpful or iatrogenic).

3. Procedures

3.1. Research Design. A two-arm randomized controlled simulation design will be employed in both parts of this proposed research. Participants will be randomized using stratified blocks of 6 or 8 participants, per recommendations by Krenan et al. (1999), based on gender and suicide attempt history (no history of suicide attempts, history of one suicide attempt, or history of multiple suicide attempts).

3.2. Sample. A sample of 150 Veterans will be included in the study and randomized to study conditions (75 in the clinician-administered CRP condition and 75 in the self-administered CRP condition). Results of a priori power analyses conducted using G*Power software (Faul et al., 2007)

indicate that a total sample of 150 will results in a highly-powered study ($\beta = .98-.99$) to detect medium-sized effects in all regression-based analyses, assuming moderate correlations amongst the seven daily measurements for this proposed study. Therefore, although we anticipate low attrition from this study, the proposed sample size is sufficiently powered for the proposed analyses, even when conservatively assuming a 20% attrition rate observed in longitudinal efficacy trials of the CRP (Bryan et al., 2017). Online recruitment methods for the study are include web-based survey and research recruitment systems (e.g., SurveyMonkey), listservs and forums, and social media sites (e.g., Facebook, Twitter, Reddit). Additionally, we are requesting use of ResearchMatch (RM), which is an NIH sponsored national registry for research volunteers. ResearchMatch (RM) and OSU have had a fully executed agreement since August 2009. The IRB of record for ResearchMatch is Vanderbilt University. The Principal Investigator will be authorized to recruit study participants.

We will enroll any prospective Veteran meeting inclusion criteria (18 years of age or older, US military veteran, death or suicidal ideation/suicide attempt within the past month) in the proposed study. Exclusion criteria include: non-Veteran status, acute intoxication or active psychosis precluding provision of informed consent, an inability to communicate and comprehend English, residence outside the United States, and lack of past-month death/suicide ideation or attempt. Participants recruited through web-based survey and research and recruitment systems will provide consent for study personnel to initiate contact through email or phone call, while those recruited through other online methods (e.g., listservs, forums) will be provided contact information for study personnel in order to inquire about the study or schedule participation.

3.3 Measurement/Instrumentation. The following self-report measures will be administered through Qualtrics online survey software during baseline procedures as part of the proposed research:

Visual Analog Scale - Participants will be instructed to reflect on their urges for suicide using the Suicide Visual Analog Scale (S-VAS; Bryan, 2019) The S-VAS assesses “urge to kill myself” using a horizontal line with anchors on the left reflecting “none” (score: 0) and on the right reflecting “extreme” (score: 100). The S-VAS is initially presented with the indicator on the “none” position, and non-movement of the indicator is followed by a prompt to remind the participant to move the indicator, if relevant, to ensure response accuracy

The Patient Health Questionnaire Depression Scale (PHQ-2; Arrol et al., 2010). The PHQ-2 is a 2-item measure of depression symptom severity adapted from the 9-item version of the PHQ (Kroenke & Spitzer, 2002). Item responses are scores on a Likert scale ranging from 0 to 3, with higher scores indicating greater symptom severity. This version of the PHQ was chosen in lieu of the PHQ-9 in order to omit an item about suicide risk contained on the PHQ-9 and decrease participant burden.

Positive and Negative Affect Schedule – Short Form (PANAS-SF; Mackinnon et al., 1999) is a 20-item validated self-report measure of state positive and negative affect. In the current study, the PANAS-SF will assess past-day positive and negative affective states.

3.3.1 Daily surveys. Prior to completing the CRP and once daily for seven days following completion of the CRP, participants in both conditions will be emailed a secure link to a Qualtrics survey including the following questionnaires:

Visual Analog Scale – See above.

Patient Health Questionnaire – 2. See above

Positive and Negative Affect Schedule – Short Form. See above.

Crisis Response Plan Use – In order to assess whether CRP use after completion impacts suicide urges and affect, participants will be instructed to “Please list all dates and times that you used part or

all of the Crisis Response Plan that you completed since you last completed this survey. (or since you completed your Crisis Response Plan if this is the first survey you will complete)" You may provide us with your best estimates of dates and times."

3.4. Informed Consent and Confirmation of Eligibility

Informed consent will be obtained through Qualtrics survey software from each participant prior to initiation of study tasks. Study personnel will obtain informed consent from participants and answer questions about the study or informed consent process prior to beginning study activities. Following informed consent, participants will complete a demographics questionnaire through Qualtrics that also includes items assessing history of suicide attempts from the Self-Injurious Thoughts and behaviors Interview (Nock, Holmberg, Photos, & Michel, 2007) for study eligibility determination and randomization purposes as well as the Suicide Visual Analog Scale (Bryan, 2019). Regardless of eligibility, all participants will be provided with contact information for crisis resources including the National Suicide Prevention Lifeline and Veterans Crisis Line.

3.5. Randomization to Study Conditions.

REDCap, a secure online survey and data management system maintained by The Ohio State University, will be utilized to randomize participants to study conditions in both components of the study immediately after obtaining demographic information (man, woman, other) and information about suicide attempt history (no suicide attempts, one suicide attempt, more than one suicide attempt) obtained from the SITBI. Participants will be randomized using stratified blocks of 6 or 8 participants, per recommendations by Krenan et al. (1999). After randomization, each participant will complete the remainder of the research study, but will be presented with one of the following pages containing instructions for completing the CRP:

Self-Administered CRP: In this condition, participants will be presented with instructions for completing and printing off the CRP. They will be directed to type in their responses onto the Qualtrics page and upload a picture of their CRP.

Clinician-Administered CRP: In this condition, study personnel will guide participants through the CRP protocol, outlined by Bryan and Rudd (2018). Participants will be directed to a Qualtrics page instructing them to collaborate with study personnel to develop a personalized CRP. Study personnel will take a screenshot picture of the CRP and upload it to Qualtrics.

3.6. Additional incentives following completion of the first portion of the study.

Following the study session, all participants will receive payment in the form of \$50 for participation. Additional incentives will be described to participants at the beginning of the study as part of the informed consent process, and administered no later than two weeks following completion of the study protocol:

3.4. Detailed Study Procedures. One hundred and fifty adult military Veteran participants residing in the United States will complete study components during the baseline study session: consenting, demographics survey and self-reported history of suicide attempts, randomization to study conditions, and the CRP. Consenting procedures will always be completed first, and demographic and suicide attempt history data will always be collected second for randomization to conditions of the study through REDCap online software. We estimate that the total participation time will be approximately 1 hour. Participants will be active in the study for eight days. In order to protect participant confidentiality, password-protected Zoom or phone-based sessions will be conducted during the baseline session and to administer the CRP to individuals in the clinician-administered CRP condition. All data will be collected through the Qualtrics, and non-PHI demographic information will be entered into REDCap system for randomization purposes. ID numbers will be linked to all data collected in the study, including identifying information collected in a separate data set as part of safety procedures, which will be deleted at the conclusion of the study. All deidentified data will be downloaded and deleted from Qualtrics servers at the conclusion of the study and stored on the

password protected OneDrive server hosted by OSU indefinitely for the proposed analyses and secondary analysis. Additionally, in order to protect participant privacy during the study, all study personnel will conduct study procedures from a private location, using a secure Internet connection and instruct all participants to do the same, if possible, and outline the risks of loss of privacy or confidentiality if the participant is unable to do so.

3.7. Internal Validity. A number of measures will be implemented to mitigate threats to internal and external validity. Specifically, the randomization procedures employed in the proposed research study (See Section 4.1.2) were selected to account for the potential influences of gender and suicide attempt status on study findings. Further, all study personnel administering the CRP will be trained to administer the protocol to maintain an average fidelity rating of 85%. A random selection of CRP sessions recorded using Zoom teleconferencing software, will be reviewed by the Principal Investigator and other trained members of the research team in order to assess fidelity to administering the protocol. If a personnel's average fidelity rating drops below 85%, they will be temporarily prohibited from administering further CRP sessions until remedial training has been completed and they obtain fidelity ratings of at least 85% for three consecutive practice administrations of the CRP.

3.8 Data Analysis. A linear mixed effects regression analysis with repeated measurements will be conducted to examine differences in suicide risk between Veterans in the clinician-administered and self-administered CRP conditions. Condition will be entered as the independent variable and outcome measures at baseline and each follow-up assessment will be entered as outcomes. These analytic procedures are consistent with previous trials examining the efficacy of the CRP (Bryan et al., 2017; Bryan et al., 2018).

3.9. Safety Procedures. The intervention under study includes two iterations of Crisis Response Planning, an intervention with demonstrated efficacy in reducing suicidal ideation and distress. Therefore, we anticipate that both versions of the CRP will demonstrate similar effects in this proposed study. Additionally, the use of crisis response plans, safety plans, and regular follow-up assessments are widely-used strategies that have been associated with decreased suicide risk and are all included in the proposed research. During enrollment in the study, all participants, regardless of agreement to participate in both portions of the study, will provide their contact information (home address, telephone number, email address) and a telephone number for an alternate person that study personnel may contact in case of imminent suicide risk. Home addresses may be used to contact the participant's local emergency services in case of imminent suicide risk. If a subject reports suicidal ideation, or a research staff member becomes aware that the subject is at imminent risk to harm himself/herself, the following questions will be asked to clarify the nature of risk (and to identify those at imminent risk requiring consideration for hospitalization): (1) Do you have a plan for killing yourself and do you intend to act on the plan?; (2) Do you have a desire to kill yourself that you believe you might act on?; (3) Have you already taken steps to act on your plan? If so, what steps have you taken? Both iterations of the CRP, which is a recommended and empirically-supported strategy for reducing suicide risk, will include contact information for professional resources and crisis services, the National Suicide Prevention Lifeline phone number, and other local behavioral health clinics and emergency departments. These procedures have been used successfully by our research team in dozens of studies with acutely suicidal individuals, to include multiple clinical trials. All participants will be provided with contact information to use in case of crisis (National Suicide Prevention Lifeline, emergency services), regardless of whether individuals choose to participate in developing the CRP.

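### Section 3.8 enters baseline as an outcome with condition as the only stated predictor; a day 1–7 contrast adjusted for baseline would be undiluted and more precise

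*Combined protocol and SAP*

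**What the plan says.** Section 3.8 (Data Analysis) is the whole analysis plan. It calls for a linear mixed-effects regression with repeated measurements, and then: "Condition will be entered as the independent variable and outcome measures at baseline and each follow-up assessment will be entered as outcomes". It adds: "These analytic procedures are consistent with previous trials examining the efficacy of the CRP". The model used in those trials is not reproduced, so it cannot be checked here whether it had time terms. No section states a time effect, a condition-by-time effect, a baseline covariate or the contrast of interest.

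The surrounding sections give the design:

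- **Schedule.** Section 3.3.1 collects the outcomes "Prior to completing the CRP and once daily for seven days following completion of the CRP", which is one pre-CRP and seven post-CRP occasions.
- **Power.** Section 3.2 plans 75 participants per arm and states power of .98–.99 (written as β) for a medium effect, "assuming moderate correlations amongst the seven daily measurements for this proposed study". That is seven measurements, whereas section 3.8 enters eight. Section 3.2 also allows for 20% attrition.
- **Baseline timing.** Section 3.4 (Informed Consent) has the post-consent questionnaire collect attempt history "for study eligibility determination and randomization purposes as well as the Suicide Visual Analog Scale", so that S-VAS precedes allocation. Section 3.3 lists the PHQ-2 and PANAS-SF among the baseline measures, but their place relative to randomisation is not given. Section 3.4 (Detailed Study Procedures) lists the session as "consenting, demographics survey and self-reported history of suicide attempts, randomization to study conditions, and the CRP" and does not mention them.

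**The concern.** The way the CRP is delivered cannot affect a measurement taken before it. If that measurement is an outcome and condition enters only as a main effect, the coefficient mixes a difference that is zero by design with the one of interest, and the estimate shrinks toward no difference. A main effect of day would not cure this. With complete data, day and condition are orthogonal and the condition coefficient is unchanged.

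If condition-by-time terms are intended, the dilution goes. The plan would still not say whether the target is the follow-up mean, the change from baseline or a slope, and neither of the first two makes the best use of the baseline.

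The aim is exploratory and no hypotheses are set, so the main product is the size of the arm difference and its interval. Section 1 says that "the results of this research will inform best practices for administration of the CRP in future research and clinical contexts". Section 3.9 expects the two versions to perform alike, and a shrunken estimate would lean toward that expectation.

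**Working it through.** **Inputs from the documents.** 75 per arm; one pre-CRP and seven post-CRP measurements; 20% attrition; stated power .98–.99 with seven measurements.

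**Assumptions (not in the documents).** Medium effect d = 0.5 SD, constant over days 1–7; two-sided alpha 0.05; compound symmetry with one correlation ρ for all eight occasions. Power is from the noncentral t with 148 df.

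**1. The plan's own figure.** The mean of seven follow-ups has per-participant variance V7 = (1+6ρ)/7, and SE = √(2·V7/75).
- ρ = 0.4: V7 = 0.486, SE = 0.114, power 0.992.
- ρ = 0.5: V7 = 0.571, SE = 0.123, power 0.980.

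This reproduces .98–.99, so ρ = 0.4 and 0.5 are used below.

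**2. Fitted as written.** Under compound symmetry with complete data, the eight occasions are weighted equally. The coefficient estimates (0 + 7 × 0.5)/8 = 0.4375.

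**3. Per-participant variances.**
- As written: (1+7ρ)/8
- Follow-up mean: V7
- Change from baseline: V7 + 1 − 2ρ
- Baseline-adjusted: Va = V7 − ρ²

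Results for N = 150, complete data, ρ = 0.4 / 0.5:

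| Contrast | Estimate (SD) | Variance | 95% half-width (SD) | Power |
|---|---|---|---|---|
| As written | 0.4375 | 0.475 / 0.563 | 0.222 / 0.242 | 0.971 / 0.944 |
| Follow-up mean | 0.50 | 0.486 / 0.571 | 0.225 / 0.244 | 0.992 / 0.980 |
| Change from baseline | 0.50 | 0.686 / 0.571 | 0.267 / 0.244 | 0.957 / 0.980 |
| Baseline-adjusted | 0.50 | 0.326 / 0.321 | 0.184 / 0.183 | >0.999 / >0.999 |

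The variance ratio to the adjusted contrast is 1.49 / 1.78 for the follow-up mean and 2.11 / 1.78 for change. Matching the adjusted precision of 150 participants would take 150 × 1.49 ≈ 224 or 150 × 1.78 ≈ 267 with the follow-up mean, and 316 or 267 with change. Simulation (8,000 replicates) gave mean estimates of 0.438 / 0.440 as written and 0.500 / 0.501 adjusted.

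**4. Attrition.** Suppose 20% leave straight after baseline and their baseline rows stay in (60 completers and 15 baseline-only per arm). A completer carries information 8/(1+7ρ), and a baseline-only participant carries 1. At ρ = 0.5:
- Total information per arm: 60 × 1.778 + 15 = 121.7.
- Baseline weight: (106.7/8 + 15)/121.7 = 0.233, against 0.125 with complete data.
- Estimate: 0.5 × (1 − 0.233) = 0.384; power 0.843 (118 df).

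At ρ = 0.4 the weight is 0.218, the estimate 0.391 and power 0.903. The adjusted contrast in completers (variance 2Va/60) has power 0.997 / 0.998.

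**5. Other correlation patterns, complete data.**
- AR(1): the baseline weight as written is 1/(8 − 6ρ) = 0.179 / 0.200, so dilution is greater, but power is 0.999 / 0.993. The variance ratio to adjusted is only 1.03 / 1.06 for the follow-up mean, and 3.93 / 3.25 for change.
- Follow-up ρ = 0.5 with baseline correlation 0.2 or 0.3: the follow-up-mean ratio is 0.571/(0.571 − 0.04) = 1.08 or 0.571/(0.571 − 0.09) = 1.19.
- Compound symmetry, ρ = 0.3 / 0.7: power as written 0.990 / 0.873; the follow-up-mean ratio is 1.29 / 2.94 and the change ratio 2.58 / 1.36.

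**6. If the target were a linear day-by-condition slope (days 0–7).** A constant post-CRP effect of 0.5 gives slope 1.75/42 = 0.0417 per day with variance 2(1−ρ)/(42 × 75). Power is 0.56 / 0.64. This figure depends on the effect being a step.

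**The case against.** The strongest reply is that section 3.8 is a short summary, and that silence about time terms does not exclude them. It names no random effects or covariance structure either. Entering baseline as an outcome makes most sense if change over time is to be compared, and the plan defers to earlier trials. On that reading there is no dilution, both the follow-up mean and the change contrast are valid, and the stated power is met for the day 1–7 mean. This stands, which is why the dilution is stated only for the model fitted as written.

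The size of the precision gain is also open to challenge. The equivalents of 224 to 316 participants need baseline to correlate with day 7 as strongly as adjacent days do. Section 3.2 assumes moderate correlation only among the daily measurements. Under AR(1), or with a weaker baseline correlation, the gain over the follow-up mean falls to 3–6% or 8–19%. This stands too. However, equal correlation is what reproduces the stated power, adjustment helped in every case computed, and under AR(1) its advantage over change from baseline is larger.

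The attrition case is severe for an eight-day study that anticipates little loss, and power as written remains at least 0.84 in it for ρ 0.4–0.5. Finally, no section makes the day 1–7 mean the target. It is proposed here because it is the contrast that reproduces section 3.2's power.

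**Conclusion.** The concern holds. Fitted as written, section 3.8 understates the post-CRP difference by 12.5% under compound symmetry, complete data and a constant effect. The understatement is 18–20% under AR(1) and 22–23% if a fifth of participants give baseline only (ρ 0.4–0.5). If condition-by-time terms are intended, the estimate is sound but less precise than the same data allow. The variance excess of the follow-up mean ranges from 3–6% (AR(1)) to 49–78% (equal correlation); for change from baseline it is 78% or more in both patterns at these correlations.

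With complete data type I error is unaffected, and for a 0.5 SD effect power is high on either reading unless a slope is the target. At an assumed 0.3 SD the difference matters more: power is 0.64 / 0.57 as written against 0.89 / 0.90 adjusted (ρ 0.4 / 0.5, equal correlation). This should be fixed because it is cheap and protects the estimate; it does not invalidate the trial. The effect size, alpha and correlations are assumptions, and the gain is assured only for the S-VAS until the timing of the other two measures is settled.

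**What to change.** Replace the model sentence in section 3.8 with:

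> The outcomes are the seven daily follow-up measurements. Fixed effects are day (categorical), condition and the baseline value of the same measure. The target is the condition difference averaged over days 1–7; condition-by-day estimates are secondary.

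Alternatively, keep baseline as an outcome, with day and condition-by-day terms and a baseline mean common to both arms. Add:

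> The baseline S-VAS is the value collected with the pre-randomisation questionnaire. The PHQ-2 and PANAS-SF are collected before randomisation in the same session.

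The stratification factors (gender and suicide attempt history) can be added as fixed effects; the figures above take no credit for them.

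The cost is three or four sentences and slightly more analysis work, with no new visits or participants. If the PHQ-2 and PANAS-SF now follow allocation, two short questionnaires move earlier, which is a small change to the session order as well as to the analysis text. The covariate version drops participants with baseline data only; the common-baseline version keeps them.

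### Section 3.8 leaves the two stratification factors out of the model; naming them would give a correctly sized standard error for a condition main effect at almost no cost

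*Combined protocol and SAP*

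**What the plan says.** Section 3.1 stratifies the blocks "based on gender and suicide attempt history (no history of suicide attempts, history of one suicide attempt, or history of multiple suicide attempts". Section 3.5 gives the levels recorded for this purpose: "demographic information (man, woman, other) and information about suicide attempt history (no suicide attempts, one suicide attempt, more than one suicide attempt". That is three levels of each factor, so up to nine cells, with blocks of 6 or 8. Section 3.7 gives the reason: the randomisation procedures "were selected to account for the potential influences of gender and suicide attempt status on study findings".

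Section 3.8 specifies a linear mixed model in which "Condition will be entered as the independent variable and outcome measures at baseline and each follow-up assessment will be entered as outcomes". It names no stratification factor, no time term and no condition-by-time term, and no other section adds them. It also says "These analytic procedures are consistent with previous trials examining the efficacy of the CRP", but the covariates of those trials are not stated in the documents.

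**The concern.** Stratified blocks force the arms to be nearly equal on gender and attempt history, so the difference between arms varies less from one randomisation to the next. A model with condition alone does not know this. It counts the outcome variation due to the two factors as between-person noise and reports an SE that is too large.

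At stake is the width of the interval. Section 1 calls the comparison exploratory and proposes no hypotheses, and section 3.9 expects the two versions to perform similarly. The useful result is therefore the confidence interval around a probably small difference, and an interval wider than the design warrants makes similarity harder to judge.

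**Working it through.** **Inputs from the documents.** N = 150, 75 per arm; stated power .98-.99 for a medium effect (section 3.2, printed there as beta); seven daily measurements, "assuming moderate correlations amongst the seven daily measurements for this proposed study"; 20% attrition, leaving 120.

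**Assumed, because the documents give no figure.** Two-sided alpha 0.05; medium = 0.5 SD (f = 0.25); within-person correlation ρ = 0.5, with 0.3 to 0.7 as the range; the two factors explain R² = 5%, 10% or 20% of the variance in participant means.

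**1. The plan's own figure.** For a between-group effect in repeated measures, λ = N·f²·m/(1+(m−1)ρ) = 150 × 0.0625 × 7/(1 + 6 × 0.5) = 65.625/4 = 16.41. With F(1, 148), power is 0.981. At ρ = 0.4 it is 0.992. The stated .98-.99 is reproduced for ρ of about 0.4 to 0.5.

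**2. Condition main effect, mean of follow-up days 1-7, perfect balance.** SE0 = √[(4/N)(ρ + (1−ρ)/7)] = √[(4/150) × 0.5714] = 0.1234 SD, and z0 = d/SE0 = 0.5/0.1234 = 4.05.

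- SE excess without the factors: 1/√(1−R²) − 1
- Type I error without them: 2[1 − Φ(1.96/√(1−R²))]
- Power without: Φ((z0 − 1.96)/√(1−R²)); with: Φ(z0/√(1−R²) − 1.96)
- 95% half-width without: 1.96 × 0.1234 = 0.242 SD; with: 0.242 × √(1−R²)

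| R² | SE excess | Type I error without | Half-width with | Power at 0.5 SD, without to with |
|---|---|---|---|---|
| 5% | 2.6% | 4.4% | 0.236 | 0.984 to 0.986 |
| 10% | 5.4% | 3.9% | 0.230 | 0.986 to 0.990 |
| 20% | 11.8% | 2.8% | 0.216 | 0.990 to 0.995 |

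With 120 participants and R² = 20%, power goes from 0.969 to 0.980 (F test). If baseline is averaged in as an eighth occasion, which dilutes the effect to 7/8, power at N = 150 goes from 0.951 to 0.956, 0.955 to 0.964 and 0.964 to 0.979.

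**3. Simulation with incomplete blocks** (nine strata, blocks of 6 or 8, N = 150, three assumed mixes of the factors, 6,000 runs per setting). The unadjusted SE exceeds the adjusted SE by 2.2-2.3%, 5.0-5.2% and 11.4-11.6% for days 1-7. Type I error without the factors is 4.3%, 4.1% and 3.3%; with them it is 4.7%, 5.1% and 5.0%. A separate simulation at R² = 20% shows where the error lies. Without the factors the reported SE is 0.123 against an actual 0.112; with them both are 0.111. The estimator hardly changes, but its reported SE does.

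**4. Baseline adjusted for.** Let b = R² × (ρ + (1−ρ)/7). The residual variance is (ρ + (1−ρ)/7) − ρ² without the factors, and (ρ + (1−ρ)/7 − b) − (ρ − b)²/(1 − b) with them. At ρ = 0.5 and R² = 20%, b = 0.1143 and the variances are 0.3214 and 0.2892, so the SE excess is √(0.3214/0.2892) − 1 = 5.4%. At 5% and 10% it is 1.2% and 2.4%. At R² = 20% it is 7.7% for ρ = 0.3 and 3.3% for ρ = 0.7. Keeping baseline as an outcome but constraining it equal across arms gives a similar result (SE 0.0926 to 0.0878 at R² = 20%).

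**5. Condition-by-time change from baseline, free baseline means.** Additive factor terms are constant within a person and cancel. At R² = 20% with complete data the SE is 0.1235 either way; with 20% random dropout it is 0.1260 without and 0.1258 with them.

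**The case against.** The strongest reply is that nothing here is a defect. The comparison is exploratory, power for the effect the trial is sized on is already about 0.98, and every size above depends on an R² that the documents do not supply. The larger figures need R² = 20%, for which the documents offer no support. All of this stands, and it limits the point to an optional improvement.

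It can also be said that the real gap is the unstated contrast. Section 3.8 puts baseline among the outcomes and section 1 speaks of decreasing ideation and increasing positive affect, so change from baseline is at least as plausible a target as a main effect. This stands too, and the fix asks for the contrast to be named in the same place.

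A reader might infer that section 3.8 contradicts section 3.7. It does not: section 3.7 speaks of the randomisation procedures, and stratified blocks do account for the factors by design. The earlier trials that section 3.8 refers to may also have included such covariates; the documents do not show it either way.

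The opposite overstatement, that the factors can never help a change-from-baseline analysis, does not hold either. Step 5 covers additive terms with free baseline means. If the factors predicted change itself (an assumed 20% of its variance), factor-by-time terms would cut the SE from 0.135 to 0.124.

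**Conclusion.** The point holds as an optional improvement. For a condition main effect, the condition-only model reports an SE about 3%, 5% or 12% too large if the factors explain 5%, 10% or 20% of participant-mean variance. With baseline adjusted for or constrained equal, the excess is about 1%, 2% or 5% at a correlation of 0.5, and up to about 8% at 0.3 with R² = 20%. For change from baseline with free baseline means and additive terms it is essentially zero.

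A reader might infer inflated false positives, an underpowered trial or wasted stratification. The documents and the arithmetic support none of these. The error is in the conservative direction, power for a medium effect over days 1-7 at N = 150 moves by at most about 0.5 point, and the blocks deliver their precision whether or not the model recognises it. What is gained is an interval of the right width. The sizes rest on the assumed R², correlation and alpha. Dropout was simulated only as unrelated to the factors, so nothing is claimed about dropout that depends on them.

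**What to change.** Add to section 3.8: *Gender and suicide-attempt history, as used in the randomisation, will be included as fixed effects in every outcome model; a gender level too sparse to estimate will be merged by a rule fixed before outcomes are examined.* State there also whether the target contrast is the condition main effect or condition-by-time.

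Main effects suffice; the nine cells are not needed. No new data are required, since both factors are collected before randomisation (section 3.5 and section 3.4, Detailed Study Procedures). The cost is at most 4 of 148 participant-level degrees of freedom. If the factors predict nothing, the SE of a main effect rises by about 0.3-0.4%. The merging rule for sparse levels still has to be written.
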